[name] has been a partner in knowledge translation and a key co-investigator in our TAPER program for many years. She is a consumer advocate who has had personal experiences with navigating medications and care of frail older adults, and contributes to a number of provincial and national committees working on polypharmacy. Her work focuses on the frail elderly, and issues surrounding pharmacology, polypharmacy and medication safety. A consumer advisory group lead by [name] has been involved in developing the TAPER intervention, and will be involved in the planning and execution of this research project. The group is comprised of patients and caregivers with lived experience in deprescribing and other aspects of the healthcare system. The group has been involved in the development and selection of tools to be used in the data collection for the feasibility study as well as knowledge translation of findings, and will continue this role in the RCT feasibility study. The advisory group will meet via skype with the research team once a month to discuss the study and provide feedback.

Focus groups will be carried out with families and caregivers of participants to gather feedback of their lived experience with the study process and gather their input into processes for incorporating their views into the TAPER process for their family member. Three focus groups will be held with 7 family members and/or caregivers in each group. The findings from the focus groups will be used to inform the future RCT.

Section 8 - Knowledge Translation

8.1: Potential for Knowledge Translation/Knowledge Mobilization/Commercialization

Describe the opportunities for knowledge translation and exchange and/or technology transfer or commercialization of the research proposed along a continuum leading to social or economic impacts or policy and practice change. If there are specific companies or organizations that will be involved, list in Section 3 (Partnerships) and ensure that a letter of support is included.

The project has integrated knowledge translation (KT) at a micro-level with clinicians and consumers participating in the design and implementation of the study. They contributed through focus groups and individual comments, to tool development around patients priorities and challenges, and to the web-based evidence support, and pathway. This has created a model and tool that is immediately scalable and responsive to emerging evidences. Knowledge will be shared at the LTC site level and with the regional network of LTC facilities, with whom we have a close collaboration (DM JV and HS) in order to disseminate fundings and initiate processes and policy changes with a wider reach. At the macro-level, TAPER investigators work closely with the Canadian National Deprescribing Network (CaDeN) to inform development of the national strategy for deprescribing. We will present findings to CaDeN to distribute learnings and influence national policy. Study findings will be made available to the research community through open access journal publications and conference presentations.

The team uses social media as part of an integrated KT strategy. Polypharmacy videos describing the rationale, and model for TAPER have a high number of views on YouTube (2700 and more recently 700). TAPER is a pathway designed so the 'Team' stakeholders can initiate the approach to polypharmacy evaluation: we have developed the TAPER tool with consumer initiation of the process in mind. A consumer health information site (RxISK.org) has been used to disseminate information about polypharmacy [40]), and this will be a vehicle for KT to consumers. The website receives >200,000 visits/month. Testing interest with a "Could you be on too many drugs" questionnaire for consumers to take to their pharmacist or family physician, generated 1000 completions in the first month.

Our partnership with DBMA has been very successful. The TAPER tool is designed to easily integrate additional evidence resources, as they become available, and designed for seamless scale-up. If successful it is planned to progress to commercialisation, in partnership with DBMA, to support scalability and sustainability at provincial national and international levels as part of routine clinical care. (support letter attached)

8.2: KT Framework/Platform

Please identify the KT framework that will be used and how it will be implemented. The framework should be one from the April 2012 Knowledge Translation Framework for Ageing and Health from the World Health Organization (http://www.who.int/ageing/publications/knowledge_translation.pdf).

The Knowledge-to-Action framework will allow us to guide the process of adapting what we already know about TAPER in primary care as we move to test its feasibility in a different context, LTC. Tailoring knowledge to a new setting is a strength of this framework. Focus of implementing each phase of the framework will occur.

A systematic look at our outcome and process data collected during our feasibility study in primary care will be used to help inform how to adapt TAPER to LTC (*adapt knowledge to local context*). For example, key learnings have and will be shared with our partners at the LTC facility with discussion of how to use these learning in the LTC setting. Examples of learnings include the best way to support family doctors and pharmacists in using TAPERMD: in the primary care setting, partnering during first time use, using peer to peer learning was very successful in addition to training sessions. Further, learnings from our feasibility pilot in LTC will also be discussed, assessing feasibility of certain data collection tools and the process of patient consent and family engagement. This will provide rich information before implementation of this study in order to assess *barriers* beforehand and develop processes to overcome these barriers (see Section 4.1 for some barriers already identified). This ultimately will involve *tailoring* the intervention to suit the context before *implementing* the intervention. We will also have a process for identifying and addressing barriers online to course-correct the intervention as a way to *monitor knowledge use*. Our plan is to *evaluate outcomes* at baseline and 6-months as well as collate process outcomes at the end of the intervention. We would plan to use these key learnings in designing and implementing our larger RCT, using the RE-AIM framework to then study reach, effectiveness, adoption, implementation, and maintenance and including a policy environmental assessment of barriers and

facilitators to implementation in routine care. Throughout this process we will leverage the opportunities described in section 8.1 to maximise KT.

Section 9 - Supporting Information

Provide tables and figures and a list of references as necessary to support sections above.

Document appended to the end of the application

Section 10 - Partnerships & Letters of Support

- Complete the table below.
- In a single PDF document please provide letters of support for each partner, collaborator etc. Upload this document below. Make sure that each letter of support within the PDF is on the organization's letterhead, detailing the partnership and specifically indicating their cash and/or in-kind contribution. The letter should specifically include reference to CFN, the proposed study, and any conditions placed on funding. See Application Instructions for guidance on allowable expenses and eligible partners and contributions.
- Individuals from the partner organizations that will be participating as project team members must be listed in the submitted Project Team Information document.
- All financial information provided in the table below must also appear in the submitted budget document.
- Where a researcher has a "financial interest" (as defined by NCE Conflict of Interest Guidelines) in a partner, the potential conflict of interest should be declared in the table. This does not preclude the partnership in any way, but provides transparency during the review process. Please see CFN Conflict of Interest Policy and Guidelines for additional guidance <http://www.cfn-nce.ca/media/23963/cfn-conflict-of-interest-policy.pdf>

Partner Organization/Research Receptor	Potential Conflict of Interest	Role in Project and Specific Use of Contribution in Project	Nature of Contribution	Contribution Amount (CDN\$)
Data Based Medicine Americas Ltd.	No	Time, custom web development, database design, secure platform hosting, software licensing, and out-of-pocket expenses	In-Kind	100000

Letters of Support

[Download CAT2017-20_Mangin_Partners.pdf](#)

Section 11 - Other Funding

For all Principal Investigators please provide details on grants currently planned, being applied for, pending and awarded, for the entire period covered by this application.

Status of Grant	Funding Source	Budget Amount of Grant	Title of Grant	% Scientific Overlap	% Financial Overlap
Awarded	CIHR	974737	Team Approach to Polypharmacy Evaluation and Reduction (TAPER)	10	0
Awarded	Labarge Optimal Aging Initiative	81500	Team Approach to Polypharmacy Evaluation and Reduction (TAPER)- Long term care (Pilot)	50	10

Supporting Documents

Project team Information

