Provide a non-confidential summary in lay terms of the CAT proposal. A lay summary is an overview of a research project described in a way that can be easily understood by those without prior experience of the subject. See Appendix A for CFN's DRAFT - Guidelines for Writing a Lay Summary

Polypharmacy (the use of many medications) is associated with poorer health and drug side effects in older adults. This makes it a concern in long-term care (LTC). We have developed a program (TAPER) for reducing polypharmacy and drug side effects for older adults living in the community. TAPER combines family doctors and clinical pharmacists, with support from the best medical evidence, and patient preferences for treatment. In this study, we will test TAPER in LTC residents. Our focus is whether using TAPER can reverse medication-related mobility problems and prevent falls. We will also explore family members' perspectives on how best to include their views in the TAPER process.

Study participants from two LTC facilities will be put into either an intervention or comparison group at random. We will assess the logistics of the TAPER process in LTC settings as well as patient outcomes including falls, thinking ability, quality of life, mobility, as well as hospitalizations and number of medications. These measures will be collected before and after the program to see if there have been changes for those receiving TAPER compared to a comparison group.

We will use these results to design and gain funding for a much larger research study to test whether this process can improve outcomes for residents when implemented as part of routine care in multiple settings across Canada. We envision a routine preventive system for screening to reduce polypharmacy and side effects in older adults - one that fits alongside immunizations and other screenings.

2.2: Scientific Summary

Provide a non-confidential scientific summary of the CAT proposal, highlighting the hypothesis, study objectives, milestones and deliverables and potential socioeconomic impact. (For funded CAT proposals, this summary will be used externally in media releases, communications and posted on the CFN's website.)

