1. Examine important feasibility measures and extent of implementation of the TAPER polypharmacy intervention in 2 LTC facilities
2. Examine signals of effectiveness of TAPER in LTC
3. Test measures for use in a larger randomised controlled trial
4. Collect data from family members to understand how to involve them in the deprescribing process, as well as their perspectives on the deprescribing process

3.4: Methodological Approach

- Describe how this project will be managed overall and who specifically will manage each major aspect of the study.
- Describe the overall study design, approaches, procedures and methods used in the study and why they are appropriate to meet the goals and objectives and deliver upon the proposed output(s).
- For example, if relevant, include aspects of participant recruitment, methods and tools used to assess participants for frailty, data collection, statistical analysis, etc.

Note: Study protocols must include frailty assessment of all study participants using a published frailty assessment instrument appropriate for the care setting.

Methods

Design

This is a feasibility RCT (1:1 patient randomization to either receive TAPER or usual care). The control group will be offered TAPER after 6-month outcomes are collected. In our experience using a randomized design in a full feasibility study is essential to ensure subsequent effective implementation in a large multi-site pragmatic RCT. This approach enables use of data in subsequent meta-analysis. Detailed testing of the proposed quantitative measures in this population is essential as score distributions may be clustered due to population characteristic similarities. In order to understand how to incorporate family and patient perspectives in priority setting, our experience with developing the approach for integrating patient priorities for TAPER in community-dwelling older adults indicates formal qualitative methods are best in developing the approach and producing publishable information for use by others working in the area.

We will randomize 90 patients (allowing for 10 dropouts). Participants will be 70 years or older and on > 5 medications. Based on our feasibility RCT in community-dwelling adults, this will provide adequate numbers to test feasibility of processes and provide information on outcome measure performance, recruitment rates and sample size calculation for a larger trial.

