Adverse effects will be addressed within the usual care clinical setting. Clinical follow-up will be determined according to the particular drugs discontinued and recorded in the web-based clinical pathway.

Frailty Measure

A validated measure of frailty (Edmonton Frail Scale) will be assessed at baseline and 6-months to determine signals of effectiveness of TAPER compared to usual care. We saw signals of improvements following reduction in polypharmacy with a statistically significant difference in the frailty measure, even in our small pilot sample in LTC [20]

See Table 1 for a full list of outcomes, timing of data collection and analysis.

Management

We have partnered with 2 LTC facilities in Brampton, Ontario, each supported by in-house primary care clinicians and pharmacists. We have an excellent working relationship with these facilities after our pilot study. The Medical Director is a co-investigator and key liaison. DM will manage the operation of the study. Regular team meetings with the McMaster research team, Medical Director (JV) and involved staff, training pharmacists to review progress will occur. Research staff will help to ensure fidelity of data collection, with double data entry among a random sample to test accuracy. Randomization and statistical analysis will be carried out by the Biostatistics Unit at St Joseph's Healthcare Hamilton (LT).

3.5: Research Outcomes, Deliverables and Milestones

- *Describe all milestones and anticipated deliverables, outputs and outcomes for the duration of the project.*
- *Provide a project schedule with dates for all milestones and anticipated deliverables, outputs and outcomes for the duration of the project, including all knowledge translation activities.*

Note: The project schedule is mandatory and will be used to track progress of the study.

- *Describe how this project will be managed and deliverables tracked.*

Demographic information such as age, sex, gender, date of birth, and ethnicity will be self-reported in the baseline data collection session in order to describe the sample.

Feasibility Measures (Research Question 2)

Feasibility measures will be assessed using recommendations of Thabane et al. (2010) [22]. Process, resources, management, and scientific areas of feasibility will be assessed through research team and administrative records for the study, and will include:

1. Long-term care recruitment rate
2. Participant recruitment, retention, refusal rates

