3. Number of cancelled-scheduled appointments
4. Proportion meeting eligibility criteria from lists generated by administrative personnel (>70 years and 5+ medications)
5. Proportion needing substitute decision maker involvement
6. Time needed for enrolment target of 80 participants

7. Length of time to complete measures
8. Performance of measures, looking for floor and ceiling effects and change over time
9. Research team's description of appropriateness of the collection surveys and process of data collection
10. Changes to process to meet context demands and needs

Study Measures (Research Questions 1,3,4,5)

Main outcome measures will be collected at baseline and 6-months post-intervention. Additional follow-up by the research team will occur at 1-week, 3-months, and 6-months after initial appointments to facilitate recall and recording of any immediate effects revealed by discontinuation. Study measures include:

1. *Mean number of medications per participant* (primary outcome of interest).
2. *Adverse events* will be collected by solicited enquiry as well as spontaneous patient or clinician report, and serious adverse events reported as a subgroup.
3. *Quality of life* will be measured by the EQ-5D-5L and SF-36 [23]. The EQ5D-5L survey will also be used in our economic analysis [7].
4. *Level of physical functioning impairment* will be measured using the Mantis.
5. *Timed Up and Go* and timed 8-foot walk test will be used as performance measures of physical functioning [24].
6. *Number of falls* (minor and those resulting in injury) will be recorded by self-report and from electronic medical record review.
7. *Pain* will be measured using the Brief Pain Inventory (short-form) [25].
8. *Performance in activities of daily living* (ADL) will be measured using the Barthel Index [26].
9. *Mobility-related fatigue* will be measured by the Avlund Mob-T Scale [27,28].
10. *Sleep* will be measured by a single item on the 15-D quality of life scale [29].
11. *Grip strength* will be assessed using a hand grip dynamometer as per standard testing procedures [30].
12. *Functional ability* will be measured using the Functional Ability Scale for the Elderly [31].
13. *Frailty* will be measured by the Edmonton Frail Scale [32].
14. *Healthcare resource utilization* data will include number of hospitalizations and emergency department and urgent care visits, as well as visits to the family physician.

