15. *Perceived change in side-effects and medication related symptoms* will be self-reported at 1-week, 3-month, and 6-month follow-up.

Semi-structured interview (Research Question 6)

Patients and family members will be asked to participate in a semi-structured interview to explore their experience with deprescribing, and their views on how to incorporate families' perspectives into deprescribing and strategies to address polypharmacy in LTC residents

Data Analysis

Means and standard deviations or proportions will be calculated for demographic information and study outcomes where appropriate. Analysis will involve t-tests or Chi-squared statistics where appropriate. Qualitative data will be analyzed by descriptive methods. See Table 1 for a full list of outcomes, timing of data collection and analysis.

Project Schedule

The project will be carried out over a 16 month period. All research, analysis and KT activities will be carried out in this time period. The project PI and the Research Associate will oversee all activities and will ensure the project schedule is followed (**See Figure 2 for the Project Schedule**)

Section 4 - Project Feasibility

4.1: Feasibility

- Identify all feasibility issues, barriers, challenges and limitations to the successful execution and completion of the study. Specifically address issue related to budget constraints, time constraints, structural issues, and organizational and personnel challenges that may delay or derail timely completion of the study.
- Describe how the investigative team plans on mitigating and overcoming these barriers, challenges and limitations.

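### Facility is left out of the between-arm analysis, and the plan does not say whether randomisation is stratified by home: a modest, cheaply avoided loss of precision

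*Combined protocol and SAP*

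**What the plan says.** Section 3.4 (Design) gives the ratio and the unit of allocation: "1:1 patient randomization to either receive TAPER or usual care". The number is also there: "We will randomize 90 patients (allowing for 10 dropouts". The lay summary says where residents come from: "Study participants from two LTC facilities will be put into either an intervention or comparison group at random". Section 3.4 (Management) adds "We have partnered with 2 LTC facilities in Brampton, Ontario, each supported by in-house primary care clinicians and pharmacists" and assigns randomisation and analysis to a biostatistics unit. Strata, blocks, minimisation, sequence generation and concealment are not mentioned.

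For the analysis, Section 3.5 (Data Analysis) says "Analysis will involve t-tests or Chi-squared statistics where appropriate". Table 1 gives a t-test for the mean number of medications, with collection at baseline and six months, and t-tests or Chi-squared tests for the other quantitative between-arm outcomes. Facility appears in none of these. Neither the text nor the table says whether the t-test uses the six-month value or the change from baseline.

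**The concern.** TAPER consists of a pharmacist consultation followed by a physician consultation, and the primary outcome is a medication count. The clinicians who deliver the intervention can therefore also affect the outcome, in both arms. If prescribing habits or case mix differ between the homes, facility predicts the outcome.

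Two things follow if facility is ignored. First, between-home variance stays in the error term of a two-sample test, so the confidence interval for the effect is wider than it needs to be. The SD passed on to the larger trial's sample size calculation also absorbs that variance. Second, without strata the mix of homes can differ between arms by chance, and the number of TAPER residents in each home is left to chance as well. That second matter has some weight because one objective is to examine implementation in both facilities.

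**Working it through.** **The plan's own figure.** 90 randomised − 10 dropouts = 80, which agrees with the feasibility measure "Time needed for enrolment target of 80 participants" (though that line treats 80 as the number enrolled). No alpha, power, effect size or SD is stated, so nothing else about the sample size can be reproduced. Its stated basis is that "this will provide adequate numbers to test feasibility of processes".

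**Inputs.** From the documents: two homes, 1:1 allocation of residents, 90 randomised, 80 after dropout, unadjusted tests. Assumed: equal-sized homes, and a between-home difference of d = 0.2, 0.5 or 1.0 within-home SDs. The documents give no value for d or for the split between homes.

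**Precision lost by ignoring facility.** With a share s of residents in one home, the total variance relative to the within-home variance is 1 + s(1 − s)d². At s = 0.5 this is 1 + d²/4. The SE ratio is its square root, and 80 completers are worth 80/(1 + d²/4).

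| d | Variance ratio | SE ratio | 80 completers are worth |
|---|---|---|---|
| 0.2 | 1.010 | 1.005 | 79.2 |
| 0.5 | 1.0625 | 1.031 | 75.3 |
| 1.0 | 1.250 | 1.118 | 64.0 |

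With an 80:20 split the variance ratios are smaller: 1.006, 1.040 and 1.160.

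**Chance imbalance in facility mix.** Take arms of 45 and homes of 45, with no strata. The number x from one home in the TAPER arm is hypergeometric, and the difference in share is (2x − 45)/45. A gap of at least 15 points needs x ≤ 19 or x ≥ 26 (at x = 26, 26/45 − 19/45 = 15.6 points). The probability is 0.206, or about 21%. For a gap of at least 20 points it is 0.091. A gap of exactly 15 points would move the raw difference by 0.15 × d, that is 0.03, 0.075 or 0.15 SD.

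**Which step recovers the loss.** Simulation used 80 completers, equal homes, a true effect of 0.5 SD, two-sided alpha of 0.05 and 8,000 trials per setting. The entries are power, with type I error in brackets.

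| Allocation and analysis | d = 0.5 | d = 1.0 |
|---|---|---|
| Unstratified, t-test | 57.3% (5.0%) | 50.2% (5.0%) |
| Stratified, t-test | 57.5% (4.3%) | 51.6% (2.9%) |
| Unstratified, facility term | 59.2% (5.1%) | 59.1% (4.9%) |
| Stratified, facility term | 59.7% (5.1%) | 60.7% (5.1%) |

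The model term accounts for nearly all of the gain. Once facility is in the model, stratifying lowers the expected variance by only about 1.3% at 80 residents (1.2% at 90). Stratifying while keeping the t-test makes the test conservative. At d = 0.2 without strata, adjustment roughly breaks even: it removes a 1.0% inflation and gives back about 1.3% through imbalance.

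**The case against.** The strongest reply is that the documents are silent on stratification and do not reject it. The text is a funding application that hands randomisation to a biostatistics unit and gives no sequence detail at all. A reader might infer that allocation is an unrestricted coin toss, with arm sizes liable to drift apart. Nothing in the documents says so. That reply stands: the supportable statement is that no stratification is specified.

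A reader might also infer that the two homes have different prescribers. The wording is "each supported by in-house primary care clinicians and pharmacists", which does not say whether staff are shared. One Medical Director is named, and Section 4.1 describes the pharmacy, pharmacists and physicians at a single location. A difference between homes is plausible but not shown, so small values of d must be kept in the range.

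If the t-test is applied to change from baseline, stable differences in prescribing level largely cancel, and the relevant d is smaller. This also stands, and the plan leaves the choice open.

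A stronger reading still is that chance imbalance confounds prescriber practice with the TAPER effect. That is not supported. Unstratified randomisation is valid, the usual standard error already allows for chance imbalance, and the simulated type I error is 5.0%. Nor is a home likely to be left with very few TAPER residents: even under coin-toss allocation, a given home of 45 would have 15 or fewer in 1.8% of allocations.

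Finally, this is a feasibility trial with no stated power, so a small loss of precision defeats none of its objectives. That limits the priority of the point. It does not remove the case for a nearly free improvement.

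**Conclusion.** The point holds as a minor one. The stated analysis omits facility, and the plan does not say whether allocation is stratified by it. For equal-sized homes, the cost of ignoring facility is about 0.5%, 3% or 12% in the standard error if the homes differ by 0.2, 0.5 or 1.0 SD; these differences are assumptions. At the low end the loss is negligible, and only from about 0.5 SD upwards is it worth noticing. If allocation is unstratified with equal arms and homes, a facility imbalance of 15 points or more arises about one time in five. The consequence is wider intervals and less control over numbers within each home. The validity of the comparison is not in question.

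**What to change.** - **Analysis.** For the primary outcome and the continuous secondary outcomes, replace the unadjusted t-test with a linear model containing arm and facility, ideally also the baseline value where one is already collected. Use a facility-adjusted analysis for binary outcomes, for example a Mantel–Haenszel estimate stratified by facility.
- **Allocation.** Have the Biostatistics Unit stratify by facility, using concealed random permuted blocks of varying size. State the sequence method, the strata and the concealment procedure in the protocol.
- **Keep the two together.** Stratifying without the model term gains almost no power and makes the t-test conservative.

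The cost is one degree of freedom for facility (one more if baseline is added) and set-up of an allocation list by home. No extra residents, visits or data are needed.
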